8.1.4 Non-immune-related Adverse Events

Additionally, Pembrolizumab (MK-3475) will be withheld for other drug-related grade 4 hematologic toxicities (except for during the induction and consolidation phase), non-hematological toxicity \geq grade 3 including laboratory abnormalities that are judged as possibly or potentially related to Pembrolizumab (MK-3475), and severe or life-threatening AEs. The table below includes dose modification guidelines for other toxicities that do not appear to be irAEs.

Dose Modification Guidelines for Non-IRAE-Related Adverse Events

Toxicity	Grade	Hold Treatment (Y/N)	Timing for restarting treatment	Dose/Schedule for restarting treatment	Discontinue Subject
Hematological Toxicity	1, 2, 3	No	N/A	N/A	N/A*
	4	Yes	Toxicity resolves to grade 0-1 or baseline	May increase the dosing interval by 1 week	Toxicity does not resolve within 12 weeks of last infusion Permanent discontinuation should be considered for any severe or life-threatening event
Non-hematological toxicity NOTE: Exception to be treated similar to grade 1 toxicity 
 • Grade 2 alopecia • Grade 2 fatigue For additional information regarding Adverse Events with a potential Immune-Etiology reference Section 7.1.1.	1	No	N/A	N/A	N/A
	2	Consider withholding for persistent symptoms	Toxicity resolves to grade 0-1 or baseline	Clinical AE resolves within 4 weeks: Same dose and schedule Clinical AE does not resolve within 4 weeks: May increase the dosing interval by 1 week for each occurrence.	Toxicity does not resolve within 12 weeks of last infusion
	3	Yes	Toxicity resolves to grade 0-1 or baseline	May increase the dosing interval by 1 week for each occurrence	Toxicity does not resolve within 12 weeks of last infusion
Toxicity	Grade	Hold Treatment (Y/N)	Timing for restarting treatment	Dose/Schedule for restarting treatment	Discontinue Subject
	4	Yes	N/A	N/A	Subject must be discontinued
*Note: As severe cytopenias during induction and consolidation phase of AML therapy are expected due to Intensive chemotherapy and the underlying disease, Pembrolizumab (MK-3475) will not be held for hematologic toxicity during these parts of the protocol therapy except in situations where it is felt causing or contributing to the hematologic toxicity.					

In case toxicity does not resolve to grade 0-1 within 12 weeks after last infusion, protocol treatment should be discontinued. With Protocol Principal Investigator agreement, subjects with a laboratory AE still at grade 2 after 12 weeks may continue treatment in the trial only if asymptomatic and controlled. Patients who experience a recurrence of the same severe or life-threatening event at the same grade or greater with re-challenge of Pembrolizumab (MK-3475) should be discontinued from protocol treatment.

8.2 Commercial Agents

Below are proposed guidelines for adjustments, but investigators should determine the most appropriate course of action based on the specifics of the situation and circumstances for each individual patient.

8.2.1 Cytarabine

Hepatic Impairment

Dosage should be modified depending on clinical response and degree of hepatic impairment, but no quantitative recommendations are available.

Renal Impairment

CrCl >60 mL/min: no dosage adjustment needed.

CrCl ≤60 mL/min: increased risk of cerebellar and cerebral toxicity with high dose regimens. a recommended dosage adjustment is as follows: for a serum creatinine of 1.5–1.9 mg/dL or increase of serum creatinine from baseline of 0.5–1.2 mg/dL during treatment, reduce the dose of cytarabine to 1 g/m²/dose. for a serum creatinine ≥2 mg/dL or if the change in baseline serum creatinine was >1.2 mg/dL, reduce the dose of cytarabine to 100 mg/m²/day continuous IV infusion.

8.2.2 Daunorubicin

Hepatic Impairment

Total bilirubin 1.2–3 mg/dL: **REDUCE RECOMMENDED DOSE BY 50%.**

Total bilirubin >3–5 mg/dL: reduce recommended dose by 75%.

Total bilirubin >5 mg/dL: omit dose.

Renal Impairment

It is recommended in patients with a serum creatinine >3 mg/dL to administer 50% of the dose.

8.2.3 Idarubicin

Hepatic Impairment

Total bilirubin 2.5–5 mg/dL: reduce recommended dose by 50%.

Total bilirubin >5 mg/dL: do not administer.

Renal Impairment

Dosage adjustment is recommended in patients with a serum creatinine greater than 2.5 mg/dL, but no quantitative recommendations are available.

9 PHARMACEUTICAL INFORMATION

A list of the AEs and potential risks associated with the investigational or commercial agents administered in this study can be found in Section 10.1.

9.1 CTEP IND Agent

9.1.1 Pembrolizumab (MK-3475) NSC # 776864

Other Names: Pembrolizumab, SCH 900475, KEYTRUDA®

Classification: Anti-PD-1 MAb

Molecular Weight: 148.9-149.5 KDa

CAS Number: 1374853-91-4

Mode of Action: The programmed cell death 1 (PD-1) receptor is an inhibitory receptor expressed by T-cells. When bound to either of its ligands, PD-L1 or PD-L2, activated PD-1 negatively regulates T-cell activation and effector function. The pathway may be engaged by tumor cells to suppress immune control. Pembrolizumab (MK-3475) blocks the negative immune regulatory signaling by binding to the PD-1 receptor, inhibiting the interaction between PD-1 and its ligands.

Description: Pembrolizumab (MK-3475) is a humanized MAb of the IgG4/kappa isotype.

How Supplied: Pembrolizumab (MK-3475) is supplied by Merck & Co., Inc. and distributed by the Pharmaceutical Management Branch, CTEP/DCTD/NCI. Pembrolizumab (MK-3475) injection is a sterile, preservative-free, clear to slightly opalescent, colorless to slightly yellow solution for intravenous use. Each vial contains 100 mg of pembrolizumab (MK-3475) in 4 mL of solution. Each 1 mL of solution contains 25 mg of pembrolizumab (MK-3475) and is formulated in: L-histidine (1.55 mg), polysorbate 80 (0.2 mg), sucrose (70 mg), and Water for Injection, USP.

Preparation: Pembrolizumab (MK-3475) solution for infusion must be diluted prior to administration. Do not shake the vials. Do not use if opaque or extraneous particulate matter other than translucent to white proteinaceous particles is observed. Do not use if discolored. To prepare the infusion solution add the dose volume of Pembrolizumab (MK-3475) to an infusion bag containing 0.9% Sodium Chloride Injection, USP or 5% Dextrose Injection, USP. Gently invert the bag 10-15 times to mix the solution. The final concentration must be between **1 mg/mL to 10 mg/mL**.

Compatible IV bag materials: PVC plasticized with DEHP, non-PVC (polyolefin), EVA, or PE lined polyolefin.

Storage: Store intact vials between 2°C - 8°C (36°F - 46°F). Do not freeze. Protect from light by storing in the original box.

If a storage temperature excursion is identified, promptly return Pembrolizumab (MK-3475) to between 2-8°C and quarantine the supplies. Provide a detailed report of the excursion (including

documentation of temperature monitoring and duration of the excursion) to [contact] for determination of suitability.

Stability: Refer to the package label for expiration.

Administer prepared solutions immediately after preparation. If not administered immediately, prepared solutions may be stored refrigerated for up to 24 hours. Pembrolizumab (MK-3475) solutions may be stored at room temperature for a cumulative time of up to 6 hours. This includes room temperature storage of liquid drug product solution in vials, room temperature storage of infusion solution in the IV bag, and the duration of infusion.

Route of Administration: IV infusion only. Do not administer as an IV push or bolus injection.

Method of Administration: Infuse over approximately 30 minutes (range: 25 - 40 minutes) using an infusion set containing a low-protein binding 0.2 to 5 μm in-line filter made of polyethersulfone or polysulfone. Infusion rate should not exceed 6.7 mL/min. A central line is not required; however, if a subject has a central venous catheter in place, it is recommended that it be used for the infusion. Do not co-administer other drugs through the same infusion line. Following the infusion, flush the IV line with normal saline.

Compatible infusion set materials: PVC plasticized with DEHP or DEHT, PVC and tri-(2-ethylhexyl) trimellitate, polyethylene lined PVC, polyurethane, or polybutadiene

Patient Care Implications: Refer to the protocol for information on evaluation and management of potential immune-related AEs.

Availability

Pembrolizumab (MK-3475) is an investigational agent supplied to investigators by the Division of Cancer Treatment and Diagnosis (DCTD), NCI.

Pembrolizumab (MK-3475) is provided to the NCI under a Collaborative Agreement between the Pharmaceutical Collaborator and the DCTD, NCI (see Section 13.4).

9.1.2 Agent Ordering and Agent Accountability

9.1.2.1 NCI-supplied agents may be requested by eligible participating Investigators (or their authorized designee) at each participating institution. The CTEP-assigned protocol number must be used for ordering all CTEP-supplied investigational agents. The eligible participating investigators at each participating institution must be registered with CTEP, DCTD through an annual submission of FDA Form 1572 (Statement of Investigator), NCI Biosketch, Agent Shipment Form, and Financial Disclosure Form (FDF). If there are several participating investigators at one institution, CTEP-supplied investigational agents for the study should be ordered under the name

of one lead participating investigator at that institution.

Sites may order initial agent supplies when a subject has been randomized.

Submit agent requests through the AURORA PMB Online Agent Order Processing application. Access to AURORA requires the establishment of a CTEP Identity and Access Management (IAM) account and the maintenance of an “active” account status, a “current” password, and active person registration status. For questions about drug orders, transfers, returns, or accountability, call or email PMB any time. Refer to the PMB’s AURORA website for specific policies and guidelines related to agent management; <https://ctepcore.nci.nih.gov/aurora>.

9.1.2.2 Agent Inventory Records – The investigator, or a responsible party designated by the investigator, must maintain a careful record of the receipt, dispensing and final disposition of all agents received from the PMB using the appropriate NCI Investigational Agent (Drug) Accountability Record (DARF) available on the CTEP forms page. Store and maintain separate NCI Investigational Agent Accountability Records for each agent, strength, formulation and ordering investigator on this protocol.

9.1.2.3 Material Safety Data Sheets – The current versions of the material safety data sheets (MSDS or SDS) for PMB-distributed agents will be accessible to site investigators and research staff through the PMB AURORA application. Questions about MSDS access may be directed to the PMB at [contact] or by using the dialog function in AURORA to communicate with PMB staff.

9.1.2.4 Product Quality Complaint (PQC)
A product quality complaint is defined as any suspicion of a product defect related to a potential quality issue during manufacturing, packaging, release testing, stability monitoring, dose preparation, storage or distribution of the product, or delivery system. Not all PQCs involve a study subject. Lot or batch numbers are of high significance and need to be provided where and when possible. PQC must be reported to the PMB as soon as the PQC is identified. Report PQC to PMB at [contact] or by using the dialog function in AURORA to communicate with PMB staff.

9.1.3 Investigator Brochure Availability

The current versions of the IBs for the agents will be accessible to site investigators and research staff through the AURORA PMB application. Access to AURORA requires the establishment of a CTEP IAM account and the maintenance of an “active” account status, a “current” password and active person registration status. Questions about IB access may be directed to the PMB IB Coordinator via email.

9.2 Commercial Agents

9.2.1. Cytarabine NSC # 63878

Other Names : ara-C

Chemical Name : 4-amino-1- β -Darabinofuranosyl-2(1H)-pyrimidinone

Classification: antineoplastic

Molecular Weight: 243.217 g/mol

CAS Number: 63878

Mode of Action: Cytarabine inhibits DNA synthesis. Cytarabine gains entry into cells by a carrier process, and then must be converted to its active compound, aracytidine triphosphate. Cytarabine is a pyrimidine analog and is incorporated into DNA; however, the primary action is inhibition of DNA polymerase resulting in decreased DNA synthesis and repair. The degree of cytotoxicity correlates linearly with incorporation into DNA; therefore, incorporation into the DNA is responsible for drug activity and toxicity. Cytarabine is specific for the S phase of the cell cycle (blocks progression from the G1 to the S phase).

Side Effects : Refer to drug package insert for additional information.

Side effects include:

- Cardiovascular: Angina pectoris, chest pain, local thrombophlebitis, pericarditis
- Central nervous system: Aseptic meningitis, cerebral dysfunction, dizziness, headache, neuritis, neurotoxicity, paralysis (intrathecal and IV combination therapy), reversible posterior leukoencephalopathy syndrome
- Dermatologic: Acute generalized exanthematous pustulosis, alopecia, dermal ulcer, epheles, pruritus, skin rash, urticaria

- Endocrine & metabolic: Hyperuricemia
- Gastrointestinal: Abdominal pain, anal fissure, anorexia, diarrhea, esophageal ulcer, esophagitis, increased serum amylase, increased serum lipase, intestinal necrosis, mucositis, nausea, pancreatitis, sore throat, toxic megacolon, vomiting
- Genitourinary: Urinary retention
- Hematologic & oncologic: Anemia, bone marrow depression, hemorrhage, leukopenia, megaloblastic anemia, neutropenia (onset: 1 to 7 days; nadir [biphasic]: 7 to 9 days and at 15 to 24 days; recovery [biphasic]: 9 to 12 days and at 24 to 34 days), reticulocytopenia, thrombocytopenia (onset: 5 days; nadir: 12 to 15 days; recovery 15 to 25 days)
- Hepatic: Hepatic insufficiency, hepatic sinusoidal obstruction syndrome (formerly known as hepatic veno-occlusive disease), increased serum transaminases (acute), jaundice
- Hypersensitivity: Allergic edema, anaphylaxis
- Infection: Sepsis
- Local: Cellulitis at injection site, inflammation at injection site (SC injection), local inflammation (anus), pain at injection site (SC injection)
- Neuromuscular & skeletal: Rhabdomyolysis
- Ophthalmic: Conjunctivitis
- Renal: Renal insufficiency
- Respiratory: Acute respiratory distress, dyspnea, interstitial pneumonitis
- Miscellaneous: Drug toxicity (cytarabine syndrome; chest pain, conjunctivitis, fever, maculopapular rash, malaise, myalgia, ostealgia), fever

Availability: Commercially available.

Product Description: Cytarabine is an odorless, white to off-white, crystalline powder which is freely soluble in water and slightly soluble in alcohol and in chloroform. Cytarabine is commercially available.

Preparation: Clear colorless solution. Refer to standard local procedure or the package insert for standard preparation instructions.

Storage and Stability: From a microbiological point of view, the product should be used immediately. If not used immediately, in-use storage times and conditions are the responsibility of the user and would normally not be longer than 24 hours at 2-8°C, unless dilution has taken place in controlled and validated aseptic conditions.

Route of Administration: Continuous IV, per institutional guidelines.

Additional information can be found in the package insert for cytarabine.

9.2.2 Daunorubicin NSC # 82151

Other Names : Cerubidin

Classification:

antineoplastic **Molecular**

Weight: 527.52 g/mol

CAS Number: 82151

Mode of Action: Daunorubicin inhibits DNA and RNA synthesis by intercalation between DNA base pairs and by steric obstruction. Daunomycin intercalates at points of local uncoiling of the double helix. Although the exact mechanism is unclear, it appears that direct binding to DNA (intercalation) and inhibition of DNA repair (topoisomerase II inhibition) result in blockade of DNA and RNA synthesis and fragmentation of DNA.

Side Effects : Refer to drug package insert for additional information.

Side effects include:

- >10%:
 - Cardiovascular: Cardiac failure (dose-related, may be delayed for 7 to 8 years after treatment), ECG abnormality (transient, generally asymptomatic and self-limiting; includes atrial premature contractions, ST segment changes on ECG, supraventricular tachycardia, ventricular premature contractions)
 - Dermatologic: Alopecia (reversible)
 - Gastrointestinal: Nausea (mild), stomatitis, vomiting (mild)
 - Genitourinary: Red urine discoloration
 - Hematologic & oncologic: Bone marrow depression (onset: 7 days; nadir: 10 to 14 days; recovery: 21 to 28 days; primarily leukopenia; anemia, thrombocytopenia)
 - Miscellaneous: Radiation recall phenomenon
- 1% to 10%:
 - Dermatologic: Discoloration of sweat
 - Endocrine & metabolic: Hyperuricemia
 - Gastrointestinal: Abdominal pain, diarrhea, discoloration of saliva, gastrointestinal ulcer
 - Local: Post-injection flare
 - Ophthalmic: Discoloration of tears

Availability: Commercially available

Product Description: Daunorubicin hydrochloride is the hydrochloride salt of an anthracycline cytotoxic antibiotic produced by a strain of *Streptomyces coeruleorubidus*. It is provided as a deep red sterile liquid in vials for intravenous administration only. Its molecular formula is C₂₇H₂₉NO₁₀•HCl with a molecular weight of 563.99. It is a hygroscopic crystalline powder. The pH of a 5 mg/mL aqueous solution is 4 to 5. Daunorubicin is commercially available.

Preparation: Deep red liquid. Refer to the package insert for standard preparation instructions.

Storage and Stability: Stored at 25°C (77°F); excursions permitted to 15°C–30°C (59°F–86°F). Needs to be protected from moisture.

Route of Administration: slow IV push over 10 to 15 minutes into the tubing of a rapidly infusing IV solution of 1L D5W or NS or and infuse over 15 to 30 minutes), or as per standard institutional practice.

Additional information can be found in the package insert for daunorubicin.

9.2.3 Idarubicin NSC # 256439

Other Names : Idamycin

Classification: antineoplastic

Molecular Weight: 497.494 g/mol

CAS Number: 256439

Mode of Action: Idarubicin inhibits DNA and RNA synthesis by intercalation between DNA base pairs and by steric obstruction. Although the exact mechanism is unclear, it appears that direct binding to DNA (intercalation) and inhibition of DNA repair (topoisomerase II inhibition) result in blockade of DNA and RNA synthesis and fragmentation of DNA.

Side Effects : Refer to drug package insert for additional information.

Side effects include:

- >10%:
 - Cardiovascular: Cardiac failure (dose-related), ECG abnormalities (transient; includes atrial premature contractions, S-T wave changes, supraventricular tachycardia, ventricular premature contractions; generally asymptomatic and self-limiting)
 - Central nervous system: Headache
 - Dermatologic: Alopecia (25% to 30%), skin rash (11%), urticaria
 - Gastrointestinal: Vomiting (30% to 60%), gastrointestinal hemorrhage (30%), diarrhea (9% to 22%), stomatitis (11%), nausea
 - Genitourinary: Urine discoloration (darker yellow)
 - Hematologic & oncologic: Anemia (effects are generally less severe with oral dosing), bone marrow suppression (nadir: 10 to 15 days; recovery: 21 to 28 days, primarily leukopenia, effects are generally less severe with oral dosing), thrombocytopenia (effects are generally less severe with oral dosing)
 - Hepatic: Increased serum bilirubin ($\leq 44\%$), increased serum transaminases ($\leq 44\%$)
 - Miscellaneous: Radiation recall phenomenon
- 1% to 10%:

NCI Protocol #: 10300

Version Date: April 10, 2025

- Central nervous system: Peripheral neuropathy, seizure

Availability: Commercially available.

Product Description: Idarubicin hydrochloride for injection, USP is a sterile, semi-synthetic antineoplastic anthracycline for intravenous use. Chemically, idarubicin hydrochloride is 5,12-Naphthacenedione, 9-acetyl-7-[(3-amino-2,3,6-trideoxy- α -L-lyxohexopyranosyl)oxy]-7,8,9,10-tetrahydro-6,9,11-trihydroxyhydrochloride, (7S-cis). Idarubicin is commercially available.

Preparation: 20 mg vials are reconstituted with 20 ml of water. Refer to the package insert for standard preparation instructions.

Storage and Stability: Stored at controlled room temperature, 15° to 30°C (59° to 86°F) and protected from light.

Route of Administration: slow IV push over 10 to 15 minutes into the tubing of a rapidly infusing IV solution of 1L D5W or NS or and infuse over 15 to 30 minutes), or as per standard institutional practice.

Potential Drug Interactions: Refer to drug package insert for additional information.

Additional information can be found in the package insert for idarubicin.

10 STATISTICAL CONSIDERATIONS

10.1 Study Design/Endpoints

This is an open label, randomized, phase 2 study. The study will consist of an induction, consolidation, and maintenance phase of therapy. A total of 50 patients will be included (25 patients in the intervention arm and 25 patients in the control arm).

Induction chemotherapy for AML has been demonstrated to result in MRD negative CR (not just CR) in about 50% of patients treated (Freeman *et al.*, 2013). Few large data sets of MRD negative CR exist across different subpopulations. We hypothesize that the addition of MK-3475 (pembrolizumab) to induction chemotherapy will lead to a 25% improvement of MRD negative CR/CRi after induction and one cycle of consolidation therapy compared to 7+3 and one cycle of consolidation chemotherapy alone. We expect a response rate of 75% in the intervention arm and 50% in the control arm for patients completing their respective treatments. Using intention-to-treat analysis, in open label study, with 25 patients in the intervention arm and 25 patients in the control arm and a significance level of 0.1, we have approximately 71% power to detect an MRD-negative CR/CRi response rate difference of 25% using a one-sided Z-test for two proportions.

Early safety schedule change: After the first 6 patients have been enrolled on the experimental arm, a safety review committee comprised of the study chair, the PIs of any patient who was enrolled in the experimental arm of the trial, and a representative from CTEP will review the

toxicity data to identify any concerning drug-related safety signals before enrolling further patients on the experimental arm. We will temporarily hold enrollment in the study if two or more patients of the first evaluable six patients in pembrolizumab (MK-3475) arm develop pembrolizumab-related severe toxicity during evaluability period. The evaluability period includes the first 35 days after pembrolizumab first dose, till hematologic recovery, or till starting consolidation therapy, whichever occurs first, as defined in section 9.5.1. To be considered evaluable for purposes of the early safety rule, the patient must have received at least one pembrolizumab dose. If the true toxicity rate is 50% or greater, this rule will stop the trial with probability at least 0.89. Similarly, if the true toxicity rate is 33%, this stopping rule will end the trial with probability 0.65. In the event this occurs, the study would resume with another 6-patient cohort in which pembrolizumab dosing will start on Day 21 instead of Day 8. The patient has to receive at least one dose of pembrolizumab to be considered evaluable for safety assessment for purposes of early stopping safety rule. If the altered schedule still results in unacceptable toxicity, we will discuss alternative approaches with CTEP. No enrollment may take place until this discussion has occurred and a suitable plan has been developed.

Toxicity analysis: The first six enrolled patients will be assessed for severe toxicity in the pembrolizumab arm. In the event that severe toxicity occurs in 2 or more of the first 6 patients, the study would resume with another 6-patient cohort in which pembrolizumab dosing will start on Day 21 instead of Day 8. If the altered schedule still results in unacceptable toxicity, we will discuss alternative approaches with CTEP. A formal toxicity analysis will be conducted after 25 efficacy-evaluable patients in each study arm.

Follow up: For patients who neither relapse nor die, the DOR will be censored on the date of their last evaluable disease assessment. Median RFS and DOR will be estimated with Kaplan-Meier curves with 95% confidence interval calculated based on the Brookmeyer-Crowley method. Long-term patient survival and disease status information will be collected for up to three years from first dose. An analysis of the survival and RFS data will be conducted based on the five-year follow up from date of randomization. Patients alive at the end of the follow-up period or lost to follow-up will be censored at the last date the patient is known to be alive. Continuous variables will be expressed by means, standard deviations and 95% confidence intervals. Frequencies will be computed for discrete data. Bonferroni's correction will be used for multiple comparisons, if any, to protect the overall type I error rate.

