Monitoring response with MRD has been proven to be very useful and is now considered a standard practice in acute lymphoblastic leukemia (ALL), APL and chronic myeloid leukemia (CML), although its optimal use for therapeutic decisions in AML remains unknown (Santamaria *et al.*, 2007; Hughes *et al.*, 2010; Borowitz *et al.*, 2015). Nevertheless, monitoring of MRD in AML with MFC is gaining popularity as there is clear evidence it refines risk assessment, and allows for long term monitoring for detection of early relapse (Hourigan *et al.*, 2017). In a study by the AML Cooperative Group, achievement of negative MRD by MFC during aplasia after induction was highly predictive for 5-year outcomes (Kohnke *et al.*, 2015). In two large prospective studies, the AML16 trial in the United Kingdom, and the HOVON SAKK AML 42 trial, undetectable MRD by MFC after 1 or 2 cycles of induction was significantly predictive for relapse risk and OS independent of other risk factors (Freeman *et al.*, 2013; Terwijn *et al.*, 2013). Although rates of MRD-negative CR achieved with induction therapy varies based on patient population studies and MRD detection assay used, in the two later clinical trials the percentage of AML patients with MRD-negative CR was only around 50%. Though some patients who achieve MRD-negative CR still relapse, and some patients who have detectable MRD after induction therapy can subsequently become MRD-negative and achieve long-term survival, MRD negativity after induction chemotherapy is associated with better outcomes. The optimal cutoff to define MRD, the technology used for detection, the optimal timing for assessment (after induction or consolidation), and the incorporation in clinical decision making all remain undefined and are being studied in prospective clinical trials.

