We hypothesize that standard anthracycline based induction chemotherapy in combination with the anti-PD-1 antibody Pembrolizumab (MK-3475) is associated with acceptable toxicity profile and leads to an improvement in the percentage of patients with MRD negative CR. We hypothesize that standard anthracycline induction in combination with the anti-PD-1 antibody, Pembrolizumab (MK-3475), would lead to an increase in the percentage of MRD negative CR from 50% to 75% after induction and one cycle of consolidation therapy.

[figure not shown]

Figure 1. Potential synergistic effect of 7+3 induction chemotherapy and checkpoint inhibition with anti PD-1 antibody Pembrolizumab (MK-3475) in inducing an immune response against AML blasts. Figure modified from Kroemer *et al.*, (2013).

2.4.1 Standard of care assessments:

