10.2 Sample Size/Accrual Rate

A total of 50 patients (25 per arm) are planned to be enrolled in the intent-to-treat analysis, which will evaluate a 25% difference in the rate of MRD-negative CR/CRi with ~71% power and an overall, one-sided alpha level of 0.1. All patients being randomized and starting induction therapy should be included in the primary analysis.

PLANNED ENROLLMENT REPORT

Racial Categories	Ethnic Categories				Total
	Not Hispanic or Latino		Hispanic or Latino		
	Female	Male	Female	Male	
American Indian/ Alaska Native	0	0	0	0	0
Asian	1	1	0	0	2
Native Hawaiian or Other Pacific Islander	1	1	0	0	2
Black or African American	1	1	1	1	4
White	15	20	1	2	38
More Than One Race	1	1	1	1	4
Total	19	24	3	4	50

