13.1 Definitions

Evaluable for toxicity. All patients will be evaluable for toxicity from the time of their first treatment with 7+3 with or without Pembrolizumab (MK-3475)

Evaluable for objective response. Only those patients who have measurable disease present at baseline, have received at least one cycle of therapy, and have had their disease reevaluated will be considered evaluable for response. These patients will have their response classified according to the definitions stated below. (Note: Patients who exhibit objective disease progression prior to the end of Cycle 1 will also be considered evaluable). All patients starting induction therapy should be included in the primary analysis with drop-outs considered as not being MRD- for the analysis of rates.

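### The 71% power takes rates labelled for treatment completers unadjusted into an intention-to-treat test, so it holds only if the 25-point difference applies to everyone who starts induction

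*Combined protocol and SAP*

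**What the plan says.** Section 10.1 gives the planning rates: "We expect a response rate of 75% in the intervention arm and 50% in the control arm for patients completing their respective treatments". The power statement follows at once and is framed on a different population: "Using intention-to-treat analysis, in open label study, with 25 patients in the intervention arm and 25 patients in the control arm", one-sided significance level 0.1, about 71% power for a 25% difference by a Z-test for two proportions.

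Section 10.2 repeats the claim for 50 patients in the intent-to-treat analysis, "which will evaluate a 25% difference in the rate of MRD-negative CR/CRi with ~71% power", and sets the analysis population: "All patients being randomized and starting induction therapy should be included in the primary analysis". Section 13.1 gives the rule for those who leave: "All patients starting induction therapy should be included in the primary analysis with drop-outs considered as not being MRD- for the analysis of rates". Section 10.5.2 treats patients without CR/CRi after induction and first consolidation as failures.

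Section 7.1.1 takes patients without CR or CRi after induction off study, so some patients who start induction will, by design, never reach the assessment after the first consolidation cycle. Section 7.1.3 lets patients who need transplant forgo remaining consolidation.

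Elsewhere the rates carry no completer label. Section 10.1 introduces the control rate with "Induction chemotherapy for AML has been demonstrated to result in MRD negative CR (not just CR) in about 50% of patients treated", and section 2.4 hypothesises "an increase in the percentage of MRD negative CR from 50% to 75% after induction and one cycle of consolidation therapy".

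**The concern.** A rate among completers and a rate that keeps non-completers in the denominator as failures agree only if everyone completes. Section 10.1 labels its rates as the first kind and uses them as the second, with no conversion and no stated completion fraction. If the label is meant, the difference being tested is smaller than 25 points and the power is below 71%.

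No analysis uses the power figure, so the stake is interpretation. In a 50-patient trial with modest power, a non-significant result would be read against a figure that is too favourable, and a reader cannot tell from 10.1 which population the 75% describes.

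**Working it through.** **Inputs.** Rates 75% and 50%, 25 per arm, one-sided alpha 0.10, Z-test for two proportions (sections 10.1 and 10.2). Drop-outs count as not MRD-negative (13.1). The non-completion fraction d is not in the documents; I assume 5%, 10% and 20%, equal in both arms.

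**Formula.** With p1 and p2 the rates in the tested population, p̄ their mean and n = 25:

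- SE0 = √[2 p̄(1 − p̄)/n]
- SE1 = √[p1(1 − p1)/n + p2(1 − p2)/n]
- power = Φ[(p1 − p2 − 1.2816 × SE0)/SE1]

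**Step 1: reproduce the plan's figure.** p1 = 0.75, p2 = 0.50, p̄ = 0.625, SE0 = 0.1369, SE1 = 0.1323. Power = Φ[(0.25 − 1.2816 × 0.1369)/0.1323] = Φ(0.563) = 71.3%. Exact enumeration of the same test gives 70.9%. So the stated 71% uses 75% and 50% directly on all 25 patients per arm. Solving the same formula for n at 71% power returns 25 per arm, so no allowance for non-completion is built in.

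**Step 2: does the base rate alone matter?** Keep 25 points in the tested population and lower both rates: 72.5% vs 47.5% gives 70.6%, 70% vs 45% gives 70.0%, 65% vs 40% gives 69.3%. The base rate hardly matters. What matters is whether the difference is still 25 points among everyone analysed.

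**Step 3: read 75% and 50% as completer rates.** Non-completers are failures, so each rate is multiplied by (1 − d), and the difference becomes 25 × (1 − d) points.

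| Assumed d, both arms | Rates in the tested population | Difference | Power | Exact enumeration |
|---|---|---|---|---|
| 0% | 75% vs 50% | 25 points | 71.3% | 70.9% |
| 5% | 71.25% vs 47.5% | 23.75 points | 67.0% | 67.0% |
| 10% | 67.5% vs 45% | 22.5 points | 63.0% | 63.3% |
| 20% | 60% vs 40% | 20 points | 55.4% | 56.1% |

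For d = 10%: p̄ = 0.5625, SE0 = 0.1403, SE1 = 0.1367, power = Φ[(0.225 − 1.2816 × 0.1403)/0.1367] = Φ(0.331) = 63.0%.

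**Step 4: what 75% asks for on the tested scale.** MRD-negative CR/CRi cannot be more frequent than CR/CRi in the same patients at the same time point. A rate of 75% among all who start induction therefore needs at least 75% in CR/CRi before any MRD requirement. The background section on checkpoint expression in human AML samples reports CR/CRi in 23 of 32 patients (72%) with a PD-1 inhibitor added to intensive chemotherapy. The antibody, chemotherapy doses and schedule differ, so this does not show that 75% is out of reach. It does show that 75% needs a justification on this scale.

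**The case against.** The strongest reply is that nothing is miscalculated and that the scale is already fixed. The 71% follows from its inputs. The power sentence is conditional on a 25-point difference under intention-to-treat, whatever label the sentence before it carries. Section 10.2 places the 25% difference in the intent-to-treat analysis. Section 2.4 gives 50% to 75% with no mention of completers, and the 50% is introduced as a rate in patients treated. The qualifier in 10.1 may only be a clumsy way of naming the time point after one consolidation cycle.

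Most of this stands. It makes the unconditional reading of the rates the more likely intention. It does not remove the contradiction: the qualifier is in the current text, directly before the intention-to-treat sentence, and the 75% is given no justification on either scale. The 5% to 20% range is illustrative and is not an estimate of this trial's power.

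A reader might infer something stronger: because the 50% is described as a rate in patients treated, only the 75% is a completer rate, and the loss of power is much steeper. The documents do not support that. The qualifier is attached to both arms in one sentence, and splitting it would penalise the intervention arm for non-completion while sparing the control arm.

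Nor should a reader conclude that the denominator of the primary analysis is undefined. The reference in 10.1 to 25 efficacy-evaluable patients per arm only times a toxicity analysis, and the evaluable-for-response definition in 13.1 is followed in the same paragraph by the explicit rule for the primary analysis.

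**Conclusion.** The concern holds as a mismatch between the label on the planning rates and the population tested, not as an arithmetic error. The 71% is correct if MRD-negative CR/CRi differs by 25 points, 75% against 50%, among all randomised patients who start induction, as 10.2 implies. It is not the power for the effect as 10.1 words it. If both rates are completer rates, power is about 67%, 63% or 55% at 5%, 10% or 20% non-completion. This assumes equal non-completion in both arms, all non-completers counted as failures, and fractions that the documents do not supply. The conduct and analysis of the trial are unaffected; what changes is how a negative or borderline result should be read. It should be corrected because the correction is specific and cheap.

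**What to change.** Amend 10.1 and 10.2 in one of two ways, leaving sample size, test and analysis set as they are.

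- **(a)** Delete the qualifier about completing treatment. State that about 71% power assumes 75% against 50% among all randomised patients starting induction, with drop-outs counted as not MRD-negative. Justify the 75% on that scale, with reference to the 72% CR/CRi quoted in the background. This agrees best with sections 2.4 and 10.2.
- **(b)** Keep the qualifier. State one assumed completion fraction for both arms, convert both rates to the intention-to-treat scale, and restate the power (for example 63% at 10% non-completion), labelled as resting on that assumption.

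The cost is a protocol wording change. Under (a) the stated power stays at 71% but the stated assumption becomes more demanding; under (b) the stated power becomes less favourable.
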